min), Rey-Osterrieth Complex Figure Test, copy condition121 (alternate version used for post- testing, counter-balanced; approx. duration: 5 min)

3. Verbal Memory: Rey Auditory Verbal Learning Test (RAVLT)121 (alternate version used for post-testing, counter-balanced; approx. duration: 10-15 min)

4. Visual-Spatial Memory: Rey-Osterrieth Complex Figure Test, delay condition121 (alternate version used for post-testing; counter-balanced; approx. duration: 5 min)

All assessments are as stated in the Human Subject Protection pages of the attached parent NIH R21 grant. Note that numbers refer to references in the Bibliography & References Cited section of the NIH R21 grant.

4) Study Visits 4-39: Exercise Training

Duration: Three 1-hour session per week for a period of 12 weeks Location: Boston University Fitness and Recreation Center

Procedures:

The study will use a randomized controlled trial. We will assign each participant by chance to one of two study groups. One group will participate in a cardiovascular endurance training program and the other group will participate in a strength, balance, and flexibility training program. We will assign participants randomly to the two training programs (50% chance). Participants will not be informed about group assignment until the first training session at the exercise facility.

Trained and experienced exercise trainers will supervise the exercise training sessions at the BU Fitness and Recreation Center. (Note: all trainers will undergo CITI training for Human Subject Protection training and HIPAA as in our previously completed clinical trial, H-32635. Trainers will then be added to the IRB protocol prior to any exercise training). The research staff, after consultation of co-investigator [name], will monitor training progress and adherence to the exercise training program. Each exercise training group will be composed of approximately 3 to 6 participants. Morning, daytime, and/or evening hours will be available for the participant to choose from, but will depend on the number of other participants enrolled and the collective group members' availabilities.

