Measurements: upper body strength in lbs or kg (based on chest press and latissimus dorsi pulldown), lower body strength in lbs or kg (based on leg press)

3) Increased lean body mass

Measurements: Percent lean body mass from BIA (and/or skinfold measures)

4) Neuropsychological test performance: improved performance scores on tests of spatial cognition, verbal memory, visuo-spatial memory, visuo-spatial attention, and executive functions post-exercise training compared to baseline and compared to controls

Measurements: neuropsychological test scores

Data Analysis

Provide a description of your plan for data analysis. State the types of comparisons you plan (e.g. comparison of means, comparison of proportions, regressions, analysis of variance). Which is the PRIMARY comparison/analysis? How will the analyses proposed relate to the primary purposes of your study? If you are doing qualitative research please state how comparisons will be made.

Specific Aim #1:

Behavioral and Fitness Data Analysis. The primary measures for the primary cognitive task (Sternberg memory load task) are % correct and reaction times, and for fitness are estimated VO 2 max. The primary statistical analyses will be repeated-measures ANOVAs with the factors group (aerobic vs. control) and time (pre vs. post) to examine group x time interactions on the outcome measures. Posthoc tests (e.g. Tukey tests) will examine if a significant group x time interaction is due to a greater improvement post-intervention in the aerobic exercise group compared to controls. Dependent measures will be tested for normality and skewed data log-transformed. We will use an alpha of 0.05, corrected for multiple comparisons.

Univariate fMRI and Functional Connectivity Analyses. We will use SPM8 and related software for statistical analysis of fMRI data. We will estimate voxel-based Statistical Parametric Maps (SPMs)

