and compare them between and within groups with mixed-design ANOVAs. We will use baseline fitness as a covariate. Because the entorhinal cortex and the hippocampus are our primary brain regions of interest, we will use a seed-based functional connectivity approach. We will compare task-related functional connectivity: 1) pre versus post intervention, and 2) aerobic exercise versus control. We will use the psycho-physiological interaction (PPI) approach91 using the Generalized PPI Toolbox92 for SPM8. The time course from a seed region constitutes the physiological variable, and the contrast of interest (e.g. high memory load > low memory load) constitutes the psychological variable in the PPI model. Our search space will be restricted to the medial temporal lobe region. We will determine the PPI variable by calculating the voxel-wise product between the physiological and the psychological variables. We will also correlate SPMs and functional connectivity strength with cognitive test scores. Analyses will include nuisance regressors (e.g. head motion).

Specific Aim #2:

Data Analysis. See Aim #1. The behavioral outcome variables of the primary cognitive task (allocentric navigation task) are distance traveled and movement speed. Addicional outcome variables are neuropsychological test scores and spatial reasoning test scores. Analyses will be as described for Specific Aim #1. In addition, we will compare two groups that differ in relative EC volume or path integration ability (by median split) using descriptive statistics (means, confidence intervals) due to the exploratory nature/ small sample size.

Sample Size

Sample Size Justification

Approximately 94 participants will be recruited total for the study: For the exercise training program

/study intervention, approximately 84 participants will be recruited with the aim to enroll 42 participants, 21 per group; for the cognitive and fMRI pilot studies, an additional 10 participants will be recruited with the aim to enroll 5 participants in the cognitive pilot and 5 participants in the fMRI pilot. Thus, this totals 94 participants (84 + 5 + 5 = 94) required to complete the cognitive pilot, fMRI pilot, and exercise training program/study intervention.

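### The verbal-list and complex-figure tests change version between visits, but version order is not in the model, so any difficulty difference between versions adds to the error of the arm comparison

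*Combined protocol and SAP*

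**What the plan says.** Under Study Visit 3, post-MRI cognitive testing, three measures change version between visits:

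- verbal memory: "Rey Auditory Verbal Learning Test (RAVLT)121 (alternate version used for post-testing, counter-balanced"
- spatial cognition: "Rey-Osterrieth Complex Figure Test, copy condition121 (alternate version used for post- testing, counter-balanced; approx. duration: 5 min"
- visual-spatial memory: "Rey-Osterrieth Complex Figure Test, delay condition121 (alternate version used for post-testing; counter-balanced"

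Study Visit 41 repeats the Visit 3 procedures.

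Data Analysis, Specific Aim #1, sets the primary statistical analyses as "repeated-measures ANOVAs with the factors group (aerobic vs. control) and time (pre vs. post) to examine group x time interactions". Specific Aim #2 carries this over: "Addicional outcome variables are neuropsychological test scores and spatial reasoning test scores. Analyses will be as described for Specific Aim #1". The Outcomes section places neuropsychological test performance fourth among the secondary outcomes.

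Covariates are named in other places: computer experience (Visit 1 screening), motion sickness (Visit 3) and baseline fitness (fMRI analysis). Test version and version order are not named anywhere as a factor, covariate or stratum. The documents do not say that the versions are equally difficult.

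**The concern.** Counterbalancing makes version order a factor that the trial itself assigns. A participant who takes the harder version second shows less improvement than one who takes it first, whatever the training did. With only group and time in the model, that predictable shift is treated as person-to-person noise.

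At stake is the precision of the between-arm difference in change for verbal memory, visual-spatial memory and figure copy. The confidence interval would be wider, and power lower, than the design allows. If the orders happen to be even within each arm, the reported standard error is also too large for the estimate, and the test rejects less often than its nominal level.

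**Working it through.** **Inputs from the plan.** 21 per arm (42 in total); f = 0.26 on average, with f = 0.20 for cardiovascular training only; alpha 0.05; power 0.80; N = 32 for cognition (Sample Size Justification).

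**Assumed.** Pre-post correlation rho, and version difference d in units of the outcome SD. Neither is stated.

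**Step 1: reproduce N = 32.** For a 2 x 2 within-between interaction, lambda = f² × N × 2/(1 - rho), with 1 and N - 2 df. At rho = 0.5 and N = 32, lambda = 0.0676 × 32 × 2/0.5 = 8.65 and power is 0.812, so the plan's figure reproduces. Other values do not give it: rho = 0.3 needs N = 44 and rho = 0.6 needs N = 26. So rho = 0.5 is used below.

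**Step 2: convert f to a difference in change.** The arm difference is 4f outcome SDs: 4 × 0.26 = 1.04 and 4 × 0.20 = 0.80. Change-score variance is 2(1 - rho) = 1.

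**Step 3: add the version effect.** With half of participants in each order and no order term, change variance becomes 2(1 - rho) + d² = 1 + d². An order term returns it to 1, and error df go from 40 to 39.

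**Step 4: power at 21 per arm** (two-sided t-test on change, noncentral t, uncorrected alpha 0.05).

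| d | Variance without term | f = 0.26: without / with term | f = 0.20: without / with term | CI narrower with term |
|---|---|---|---|---|
| 0.2 | 1.04 | 0.897 / 0.908 | 0.699 / 0.715 | 2% |
| 0.3 | 1.09 | 0.883 / 0.908 | 0.678 / 0.715 | 4% |
| 0.5 | 1.25 | 0.837 / 0.908 | 0.619 / 0.715 | 10% |
| 0.8 | 1.64 | 0.728 / 0.908 | 0.506 / 0.715 | 22% |

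At f = 0.26 the losses are about 1, 2.5, 7 and 18 points. At f = 0.20 they are about 4 points at d = 0.3 and 10 at d = 0.5. A 5-point loss is reached at d = 0.42 (f = 0.26) or d = 0.35 (f = 0.20).

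**Step 5: vary rho.** Holding the difference at 1.04 SD and d = 0.5, power without / with the term is 0.726 / 0.793 at rho = 0.3 (7 points) and 0.946 / 0.989 at rho = 0.7 (4 points).

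**Step 6: bias and test level, by simulation.** At 16 per arm the mean estimate stayed at 1.03 to 1.04 against a true 1.04 in every setting. At 21 per arm with order balanced within arm, type I error without the term is about 4%, 3% and 1.4% at d = 0.3, 0.5 and 0.8, and about 5% with it. With order balanced only overall, the level stays near 5% but the estimate itself varies more. Power falls either way: at 16 per arm and d = 0.5 it is 0.74 (balanced within arm) or 0.72 (balanced overall) without the term, and 0.81 with it.

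**The case against.** The strongest reply is that the harm rests on an unknown. The documents do not show that the versions differ, and at d of 0.3 or less the loss at the planned effect is under 3 points. That stands.

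The enrolment margin also absorbs much of it. At f = 0.26 and 42 participants, power without the term stays at or above 0.80 until d is about 0.61. At f = 0.20 power is only 0.715 even with the term, so the smaller effect is the main shortfall there. This stands too.

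The outcomes are not the leading ones. The primary cognitive tasks are the Sternberg and navigation tasks, and fMRI is also primary. The sample size was not built on these two tests.

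It may also be said that the ANOVA sentence is not a full model specification, since covariates are promised elsewhere. That is fair, but none of those covariates is version or order.

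A reader might infer that the arm comparison is biased or that false positives rise. The documents do not support this: arms are randomised, order is counterbalanced, and any departure from the nominal level is downward. A reader might also infer that order should be assigned within arm. The baseline version is given at Visit 3, and the Study Summary appears to place randomisation after the three initial visits, so the arm would not yet be known. The order term is enough without it.

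**Conclusion.** The point holds as an inexpensive gain in precision for secondary outcome 4 and the additional Aim #2 outcomes. The primary task and fMRI analyses are unaffected, and the planned contrast is unbiased.

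The size cannot be fixed from the documents. It is negligible if the versions are nearly equivalent, and worth having from d of roughly 0.35 to 0.42 upward, where 5 power points are at stake. These figures rest on rho = 0.5, which is inferred because it reproduces the plan's N, on 21 analysed per arm, and on alpha 0.05 before the plan's correction for multiple comparisons.

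**What to change.** Record which version each participant receives at each visit. In Data Analysis, for the RAVLT and for the Rey-Osterrieth copy and delay scores, add that test's own version order (A then B, or B then A) as a between-subject factor crossed with time. Equivalently, put an order term in the change-score or baseline-adjusted model. Report the between-arm difference from that model. The crossing with time must be stated, because an order main effect alone leaves the group-by-time test unchanged.

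The cost is one sentence in the plan, a record of the version given, and one error degree of freedom (40 to 39). If the versions are equally difficult, the loss is about 0.1 power point by formula, and at most about 1 point when order is uneven across arms.

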s/he may be asked to make decisions about the presented stimuli, scenes, or environments, and to indicate responses on handheld response keys or with a joystick. Between each set of stimuli there will be a short break. We will remind the participant to keep his or her head as still as possible during task performance and the breaks in between.

We may take measurements of blood pressure, heart rate and/or pulse immediately before entering and immediately after exiting the fMRI scanner room. During fMRI scanning we may use pulse oximetry.

Outcomes

Describe anticipated primary outcome and any secondary outcomes and how they will be measured:

Primary Outcomes for Specific Aim #1:

1) Better cognitive task performance post-exercise training compared to baseline (measurements: reaction times, accuracy, etc.); effect expected to be greater for aerobic exercise training than control (strength, balance and flexibility training)

Measurements: reaction times, accuracy, and other cognitive task derived scores

2) Increased activation in and functional connectivity between brain areas associated with task performance, effect expected to be greater following aerobic exercise training than control. Measurements: blood-oxygen level dependent fMRI scans

Primary Outcomes for Specific Aim #2:

1) Better cognitive task performance post-exercise training compared to baseline (measurements: reaction times, accuracy, path length, spatial reasoning test scores, etc.); effect expected to be greater for aerobic exercise training than control (strength, balance, and flexibility training)

Measurements: reaction times, accuracy, path length, and other cognitive task derived scores

2) Increased activation in and functional connectivity between brain areas associated with task performance, effect expected to be greater for aerobic exercise training than control; this effect of aerobic exercise training will be greater for subjects with 1) smaller compared to larger relative entorhinal cortex volume, and 2) below-median compared to above median path integration skills

Measurements: blood-oxygen level dependent fMRI scans

Secondary outcomes for all aims:

1) Increased aerobic capacity for aerobic exercise group participants

Measurements: VO2max (estimated from submaximal incremental work rate test)

2) Increased strength for control group participants

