For the exercise training program/study intervention, the sample size for enrollment was determined from simulation-based power predictions for fMRI (Desmond & Glover, 2002), and based on a metaanalysis on exercise training effects on cognition in older adults (Colcombe and Kramer, 2003). 1) fMRI: Given an estimated mean difference of 0.5% signal change, a between-subject variance of 0.5%, and a statistical power of 0.80, a sample size of 11-12 subject per group would be needed for $\alpha = 0.05$ and N = 21 per group for $\alpha = 0.002$. 2) Cognition: we performed sample size calculations with G*Power 3.1.7 based on effect sizes reported in the literature. Effect sizes were f = 0.26 for a short-duration exercise intervention, f = 0.30 for session durations of 45 min, f = 0.20 for cardiovascular training only, f = 0.21 for the visuospatial domain, and f = 0.35 for participants aged 65+ years. Based on an average f of 0.26, a statistical power of 0.80, and alpha = 0.05, a total N = 32 subjects will be needed. Oversampling to 42

Risks and Benefits

Risks associated with the cardiovascular fitness and strength tests

The exercise test will require a gradual increase of exercise intensity. Because it is very strenuous to reach maximum oxygen uptake even after rest it may pose a health risk for some participants. Risks and discomforts include the possibility of adverse changes during the test, including abnormal blood pressure, fainting, dizziness, severe fatigue, body aches, heart rhythm abnormalities, stroke, and very rare instances of heart attack.

Risks and discomforts associated with the strength tests include feeling tired and experiencing muscle cramps. Other, less common, risks and discomforts include muscle tear, spraining a ligament (connective tissue) and lightheadedness.

Risks associated with bioelectrical impedance analysis (BIA)

The bioelectric impedance analysis (BIA) uses a very small electrical current, which passes between electrodes placed on the hands and/or feet. The amount of this current is slight enough that the participants will not be able to feel it and poses no risk to humans. However, there is a slight risk that this low current could disrupt an artificial pacemaker or defibrillator.

Risks associated with exercise

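### The post hoc (e.g. Tukey) step after a significant group x time interaction cannot answer the directional question given to it; the interaction estimate already does

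*Combined protocol and SAP*

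**What the plan says.** The Data Analysis section for Specific Aim #1 (Behavioral and Fitness Data Analysis) specifies "repeated-measures ANOVAs with the factors group (aerobic vs. control) and time (pre vs. post) to examine group x time interactions on the outcome measures". It then adds a follow-up: "Posthoc tests (e.g. Tukey tests) will examine if a significant group x time interaction is due to a greater improvement post-intervention" in the aerobic arm than in controls. On error control it says only "We will use an alpha of 0.05, corrected for multiple comparisons", without naming the family or the method.

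The Outcomes section states the hypothesis in the same terms: better performance after training than before, with the "effect expected to be greater for aerobic exercise training than control (strength, balance and flexibility training").

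The Specific Aim #2 paragraph carries the plan over: "Analyses will be as described for Specific Aim #1".

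The plan does not say which means the post hoc tests compare, which error term they use, or what is concluded if a significant interaction is followed by a non-significant post hoc test.

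**The concern.** Whether the aerobic arm improved more than the control arm is the trial's main question for these outcomes. In a design with two arms and two visits, the interaction answers it directly, because the contrast is aerobic change minus control change. The plan hands the same question to a second procedure.

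A Tukey test on group alone or on time alone has only two levels and adds nothing, so its natural use here is on the four arm-by-visit means. That gives six pairs. Two are pre versus post within an arm, and four compare different participants. None of the six is a difference in change.

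Two things are at stake. A significant, favourable interaction may be followed by a non-significant pairwise test, and the plan does not say what is then reported. Or a significant pairwise test may attach the wrong explanation to the interaction. The step applies to the behavioural and fitness outcomes of both aims.

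**Working it through.** **Inputs.** From Sample Size Justification: f = 0.26, power 0.80, alpha 0.05 and total N = 32 ("Based on an average f of 0.26, a statistical power of 0.80, and alpha = 0.05, a total N = 32 subjects will be needed"), with enrolment "with the aim to enroll 42 participants, 21 per group". The software is named ("we performed sample size calculations with G*Power 3.1.7 based on effect sizes reported in the literature"), but the test family and the pre-post correlation rho are not. Assumptions added here: rho, normal data, equal variances, no dropout.

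**Reproducing N = 32.** For the interaction in a repeated-measures ANOVA with m = 2 visits, lambda = f² × N × m / (1 − rho), with 1 and N − 2 df. At rho = 0.5 and N = 32, lambda = 0.0676 × 32 × 2 / 0.5 = 8.65 and power is 0.812. This is the smallest even N that reaches 0.80, so the stated figure is reproduced. Other values of rho give other N: 62 (rho 0), 44 (0.3), 20 (0.7), 14 (0.8). At N = 42 and rho = 0.5, power is 0.908.

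**Raw effect.** A difference in change of delta SD has noncentrality delta² × N / [4 × 2(1 − rho)]. Setting this equal to lambda gives delta = 4f = 1.04 SD, whatever rho is.

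**Thresholds at rho = 0.5, 21 per arm, in SD units.**
- Interaction: the SD of change is √[2(1 − 0.5)] = 1, the SE is √(2/21) = 0.309, and the threshold is 2.021 × 0.309 = 0.62.
- Tukey, error (a), four means treated as independent, 80 df: 3.71 × √(1/21) = 0.81.
- Tukey, error (b), within-subject error, 40 df: 3.79 × √(0.5/21) = 0.58.

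**Error term.** The correct SE is √(2 × 0.5/21) = 0.218 for a pre-post pair and 0.309 for a between-arm pair. Error (a) uses 0.309 for both, which is too large for the paired comparisons. Error (b) uses 0.218 for both, which is too small for the between-arm ones.

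**Different contrasts.** At rho = 0.5 the post-versus-post difference and the difference in change have the same variance, 2/21, and covariance 2(1 − 0.5)/21 = 1/21. Their correlation is therefore only 0.5, so the two tests can disagree under either error term.

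**Simulation, rho = 0.5, 21 per arm, among significant interactions favouring aerobic.**

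| Scenario | Tukey result | Error (a) | Error (b) |
|---|---|---|---|
| Only aerobic improves, 1.04 SD | Post vs post not significant | 20% | 5% |
| Only aerobic improves, 1.04 SD | Aerobic pre-post not significant | 11% | 0.7% |
| Only aerobic improves, 0.52 SD | Post vs post not significant | about 68% | about 36% |
| Only controls decline, 1.04 SD | Post vs post significant | 80% | 95% |
| Only controls decline, 1.04 SD | Aerobic pre-post significant | under 1% | under 1% |

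**Type I error.** With no interaction and a 0.5 SD practice effect in both arms, a favourable significant interaction occurs in 2.5% of trials. The same event together with the pattern that aerobic changed significantly and control did not occurs in 1.5% (a) or 2.4% (b). The extra step cannot raise the rate.

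**The case against.** The strongest defence is that the primary analysis is named and correct, and that the post hoc step is ordinary follow-up whose wording only promises to look at what an interaction is due to. Most of this stands, and it rules out four stronger readings.

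- A reader might infer that the post hoc test must be significant for the primary result to stand. No sentence says so. Used as a required gate on the post-versus-post comparison, it would cut power from 0.91 to 0.73 (a) or 0.86 (b), but the plan sets no such gate.
- A reader might infer that a wrong error term has been chosen. None is given, and Tukey is only an example. Paired within-arm tests or a contrast on change would also fit the sentence. The defect is under-specification.
- A reader might infer that the step creates false positives. It runs only after a significant interaction, so it can misexplain one but cannot manufacture one.
- A reader might infer that disagreement becomes severe at higher correlations. If interaction power is held near 91% by shrinking the raw effect to about 0.81 SD (rho 0.7) or 0.66 SD (rho 0.8), the post comparison under error (a) is significant in only about 52% and 34% of significant interactions. But f = 0.26, under the convention that reproduces N = 32, is a fixed 1.04 SD. At that effect the figures are about 80%, 77% and 77% for rho 0.5, 0.7 and 0.8.

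It is also fair that showing which arm changed is useful. What the defence does not answer is that the sentence assigns the between-arm direction to a procedure that does not test it.

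**Conclusion.** The concern holds in limited form. The post hoc step is redundant for direction, is aimed at other contrasts if done with Tukey tests, and leaves open the means compared, the error term and how a disagreement is handled. At the planned effect, disagreement on the post-versus-post comparison is about 5% to 20% of significant favourable interactions. It is larger if the true effect is half as big. The misexplanation risk is clearest when controls decline and the aerobic arm is flat.

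The primary test, its type I error, N = 32 and the power at N = 42 are unaffected, so the point is minor to moderate and not a must-fix. The figures rest on an assumed correlation of 0.5, which reproduces the stated N but is not in the documents, and on normal data, equal variances and complete follow-up.

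**What to change.** Replace the post hoc sentence under Specific Aim #1 with: 'The primary estimate is the between-arm difference in change (the group x time contrast) with its 95% CI, and its sign determines which arm improved more; within-arm changes are reported with paired 95% CIs as description only and do not alter the primary conclusion.' The existing cross-reference carries this to Aim #2.

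The sign should be read in the favourable direction for each outcome, since a lower reaction time is better and a higher percentage correct is better.

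The cost is one sentence. No new data are needed. At rho = 0.5 the required N stays 32, power at N = 42 stays about 0.91, and type I error stays about 0.05. The within-arm information that the follow-up was meant to provide is kept.

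### The connectivity paragraph names generalized PPI but describes a single-contrast PPI; run as described, an aerobic-arm activation change can, under some task designs, appear as a connectivity change

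*Combined protocol and SAP*

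**What the plan says.** The relevant text is under Data Analysis, Specific Aim #1, in the paragraph on univariate fMRI and functional connectivity. The tool is named first: "We will use the psycho-physiological interaction (PPI) approach91 using the Generalized PPI Toolbox92 for SPM8". The model follows:

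- Seed: "The time course from a seed region constitutes the physiological variable".
- Task term: "the contrast of interest (e.g. high memory load > low memory load) constitutes the psychological variable in the PPI model".
- Interaction: "We will determine the PPI variable by calculating the voxel-wise product between the physiological and the psychological variables".
- Other terms: nuisance regressors, with head motion as the example.
- Use of the estimates: "We will compare task-related functional connectivity: 1) pre versus post intervention, and 2) aerobic exercise versus control".

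Under Outcomes, the second primary outcome for Aim #1 is "Increased activation in and functional connectivity between brain areas associated with task performance, effect expected to be greater following aerobic exercise training than control". Aim #2 has a parallel primary outcome, and its data analysis refers back to Aim #1. The plan gives no design matrix, no task timing and no statement on whether the task has a rest or fixation baseline.

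**The concern.** The tool and the model sentences do not match. A generalized PPI enters one psychological regressor and one product regressor per task condition, and takes the contrast afterwards on the product coefficients. The text describes one seed, one contrast as the psychological variable, and one product. An analyst could follow either, and the two need not give the same answer.

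The difference matters because the plan expects activation and connectivity both to rise more in the aerobic arm. The connectivity test must therefore be able to tell a connectivity change from an activation change. If it cannot, the trial could report better entorhinal-hippocampal communication, which is its central mechanistic claim, when only activation had changed.

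**Working it through.** The plan attaches no figure to this model, so there is none to reproduce. The check is algebra followed by simulation.

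**Inputs.** From the documents: 21 per group (Sample Size Justification), alpha 0.05 (stated for the behavioral and fitness analysis), and the model terms above. Assumed: task timing, rest blocks, activation sizes, noise and between-person spread.

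**Algebra.** Let H and L be non-overlapping indicators of high and low load, so that H² = H, L² = L and HL = 0 (approximate after haemodynamic convolution). Let the seed be s = aH·H + aL·L + e, and let the target have activations bH and bL.

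- Product: s(H−L) = ½(aH+aL)(H−L) + ½(aH−aL)(H+L) + e(H−L).
- Target activation: ½(bH+bL)(H+L) + ½(bH−bL)(H−L).

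The described model has columns for the constant, s, (H−L) and s(H−L), but none for (H+L). Without scanned baseline, H+L equals the constant and is absorbed. With baseline, it can be picked up only through s and the product. The product carries it with weight ½(aH−aL), so the leak needs both unmodelled baseline time and a load-dependent seed.

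With activations 1.0 (high) and 0.6 (low) in both regions:

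- Before training: product weight ½(1.0−0.6) = 0.20; target common activation ½(1.0+0.6) = 0.80.
- High load +0.5 in both regions: ½(1.5−0.6) = 0.45 and ½(1.5+0.6) = 1.05. Both move, so the PPI coefficient shifts although connectivity is unchanged.
- Both loads +0.5 in both regions: ½(1.5−1.1) = 0.20, unchanged. Target common activation is ½(1.5+1.1) = 1.30, but so is the seed's, and the seed column can take up most of it.

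A target change along the contrast only, from (1.0, 0.5) to (1.25, 0.25), leaves bH+bL at 1.5 and adds no leak.

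**Simulation with scanned rest.** True connectivity change is zero, with a two-sample test on the pre-post change in the PPI coefficient. Run A used 300 volumes, TR 2 s, 24 blocks of 12 s separated by 12 s rest, between-person SD 0.4, coupling 0.3 and 600 trials. Runs B to D were built similarly; B and D had 400 trials each. Cells give rejection, described model / per-condition model.

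| High-load rise, seed and target (noise SD) | A | B | C | D |
|---|---|---|---|---|
| 0 | 6.7% / 5.0% | 3% / 3% | – | – |
| 0.25 | 11.0% / 5.7% | 11% / 7% | 15% / about 5% | – |
| 0.35 | 16.0% / 4.8% | – | – | – |
| 0.5 | 27.7% / 6.2% | 37% / 5% | 31% / about 5% | 34.5% / – |

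Changing other settings in A at +0.5, always with rest kept, moved the described model between 15% and 50%.

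A separate simulation used 240 scans, activations 1.0 and 0.5, 150 trials, and the product formed at BOLD or neural level:

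- High load +0.5 in both regions: 85% / 93% (BOLD / neural). The mean PPI estimate rose from about 0.20 / 0.22 to about 0.34 / 0.39.
- Common activation +0.5 in the target only: 59% / 62%.
- Per-condition model: mean estimate within 0.006 of zero; rejection between 3% and 8% throughout.

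**Where the leak vanishes (described model).**

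- No rest blocks: 4% to 8% in the separate simulation, 5.5% in B, 4.5% in D.
- Contrast-only change in the target, rest kept: 5%.
- Both loads rising equally in both regions, rest kept: 6.5% (A, 200 trials) and 5% (B).
- Seed with no load effect, rest kept: mean PPI estimate about 0.03.

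Monte Carlo standard error at a true 5% is √(0.05×0.95/600) = 0.9 points for 600 trials and √(0.05×0.95/150) = 1.8 points for 150.

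**The case against.** A reader might infer that the trial will run the single-contrast model. The documents do not establish that. They give no closed list of regressors, the contrast is introduced as an example, and the named toolbox points to per-condition modelling. The sentence may be a loose way of saying which contrast is tested. What stands is a contradiction between a named method and an explicit model statement.

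A reader might also infer that any aerobic-arm activation change will be tested as a connectivity change. That is too strong. The contrast term removes activation along the contrast, and the leak needs scanned baseline time and a load-dependent seed. Neither is given. The breaks described, between stimulus sets under Study Visit 3 and between runs under Risks of completing tasks, may lie outside the modelled series.

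The rates also depend on the set-up, as the spread between simulations shows. They come from one uncorrected test on one target. The plan describes voxel-based mixed-design ANOVAs with baseline fitness as covariate and a medial temporal search space. All of this limits the size that can be claimed.

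The two-load result cannot be carried over to Aim #2 as a number, because no navigation contrast or conditions are defined.

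Finally, a smaller repair exists: adding a single common-task regressor (high plus low) brought rejection back to 5.3% with rest present. It would still leave the text at odds with the tool it names.

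**Conclusion.** The concern holds in conditional form. The plan names generalized PPI and describes a different model for a primary outcome. If the described model is run, the scan includes unmodelled baseline time and the seed's response differs by load, then an activation change of the kind the plan predicts can appear as a group-by-time connectivity change.

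Under assumed rest blocks, the similarly built simulations put false rejection at roughly 11% to 37% for a high-load rise of 0.25 to 0.5 noise SD, and the separate simulation put it higher. It stays near 5% without rest, or when both loads rise equally in seed and target. These figures show direction and possible size and are not forecasts for this trial. The per-condition model stayed between 3% and 8% in every scenario tried. The text should be corrected even though the realised bias cannot be known from the documents.

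**What to change.** Replace the model sentences in the Aim #1 connectivity paragraph with text such as:

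> The PPI model contains, for each task condition, one psychological regressor and one PPI regressor (the product, at each time point, of the seed time course and that condition's regressor), together with the seed time course and nuisance regressors. The contrast (for example high minus low load) is computed on the PPI coefficients and carried to the group analysis.

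Delete the sentence that makes the contrast the psychological variable. Correct the voxel-wise description of the product at the same time. It is a minor slip: the psychological variable has no voxel dimension, so the product is taken over time points. Use the same structure for Aim #2 once its conditions are defined.

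The cost is a few sentences and no new data. A few extra regressors per participant leave slightly fewer first-level degrees of freedom. If generalized PPI was always intended, only the wording changes.
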